### Pilot study main results

To explore gamification's role in promoting social support for weight loss, our team developed a mobile app that rewards social support through social gaming. The Social Pounds Off Digitally study, a three-month randomized weight loss intervention, delivered remote content via twice-weekly podcasts. Experimental group participants ( $n=26$ ) lost more weight (-5.3 kg) than the standard app group ( $n=25$ ; -2.2 kg;  $p=0.02$ ). Total points earned predicted % weight loss ( $p=0.01$ ). This diverse study sample (39% African American) represents one of the more inclusive digital weight loss intervention studies

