### Study aims

The goal of the present study is to examine the mLife intervention in a long-term study and to isolate the use of points to gamify the intervention in order to ensure that use of social gaming leads to improvements in social support and continued weight loss.

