## **Overview of Intervention**

This is a one-year remote intervention, randomized trial that will be conducted in two cohorts. Participants will be randomized to one of two groups: 1) mLIFE+points (n=120) or 2) mLIFE (n=120). Both groups will receive the same intervention, but in order to isolate the impact of points/social gaming, the mLIFE+points group will receive points for engaging in social support-related behaviors and the mLIFE will not.

All participants will be asked to track all their meals daily via the mLIFE App, use a Fitbit to track their physical activity, and use a Fitbit scale to track their body weight. Also, all participants will receive twice weekly podcasts and daily in-app tip of the day (based on Social Cognitive Theory and modeled from the Diabetes Prevention Program). The mLIFE App will also encourage and facilitate social support among participants. The intervention will last 12 months.

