## Social support activities and gamification

The mLife app offered eight social support activities to engage users and test gamification. It automatically posted newsfeed when users logged meals, exercised, tracked weight, or listened to podcasts. Users could “like” posts and request support from peers by commenting or asking questions. Peers could comment and respond to support requests, and users received notifications when peers offered support. Refer to the graph below that shows the gamified social actions within the application id and point value for the leaderboard.

[figure not shown]

Id	Name	Point Value
3	Respond to a support request*	1
4	Outreach	1
5	Thank for thumbs up/Comment*	1
6	Request support	1
7	Thumbs up logged weight	1
8	Thumbs up logged diet	1
9	Thumbs up logged physical activity	1
10	THUMBS UP READ TIP OF THE DAY OR LISTENED TO A... 	1
12	Reply to a Comment	0

Participants are also prompted to send supportive messages to inactive peers. When inactive for more than 24 hours, an outreach request is posted in the newsfeed: “(username) hasn’t been active for more than a day. Please send them an encouraging message to return.” Participants can choose a pre-written message or create a custom message and send it via text. Pre-written messages are created using Social Cognitive Theory to target social support, self-efficacy, and outcome expectations regarding self-monitoring behavior. Once an outreach message is sent, the request is closed.

Participants earn up to 8 points per day for social support interactions. They can provide support as many times as desired, with a maximum of 1 point per activity. The mLife+Points group views the 8 activities, their daily points, and an overall leaderboard that resets monthly to boost motivation. The mLife group is unable to see the points earned; they have daily checklists. However, the mLife app calculates points for objective comparison between groups.

Posting a “request for support” comment or question in the app’s newsfeed allows mLife peers to comment and respond. Initially, participants could only post one response to peer requests to control moderation, but this limited social interactions, so unlimited responses were allowed at the 8 weeks data inspection. See the comment replies example graph below.

All participants' social interactions are posted in the newsfeed.

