### ***Aims 1 and 2***

We are powering our study to detect differences in weight loss at one year between those randomized to mLife+points and mLife groups (Aim 1) and differences in social support provision and receipt at one year between groups (Aim 2). For Aim 1 power, we used an F-test on the interaction between time (two levels) and treatment arm (two levels) in a two-way ANOVA with repeated measurements. We assumed **conservatively** a small effect size (Cohen's  $d = 0.1$ ).

Moreover, we used our NETworks pilot work, which collected weight loss outcomes at one year, to determine the intra-cluster correlation (ICC) which is the correlation of weight between times within individuals. The pilot study estimate of the ICC was 0.9 but we judged that this estimate may be too optimistic and lead to an inadequately low sample size (see Table 5). Therefore, we used a more **conservative** ICC = 0.7. In summary, we calculated that to achieve 95% power (alpha = 0.05) for Aim 1 assuming a small effect size (Cohen's  $d = 0.1$ ) and ICC equal to 0.7, we need a sample size equal to 200. Further, we assumed an attrition rate of 15-20% and increased the sample size to 240. Thus, we aim to recruit a total of 240 participants (~120 per cohort), with the initial randomization assigning 120 to mLife+points and 120 to mLife. This sample size will also give us abundant power for the study in Aim 2. Based on our Social POD pilot work, we are powering Aim 2 from both differences in overall app usage (Social POD  $50.7 \pm 25.0$  days and standard  $34.4 \pm 25.8$  days out of a possible 84 days) and points earned (representing social support provision). Social POD pilot participants earned a mean of  $202 \pm 105$  points/participant. We are assuming a difference of 50 points between groups with a SD of 105. Therefore, with the sample size chosen for Aim 1, our

power for Aim 2 will be 99% for app usage and 95% for points earned.

The sample size for our study has been chosen to ensure sufficient statistical power to detect differences in weight loss at one year after baseline between those randomized to mLife+points and mLife groups (Aim 1) and differences in social support provision and receipt and at one year between groups (Aim 2).

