### **Sample size according to F-test**

Because our main outcomes will be measured at 12 months, we are using pilot work that collected weight loss outcomes at one year. Based on our pilot data (NETworks trial as this provides 12-month outcomes for weight), as well as several other one-year mHealth intervention studies, we calculated the sample size necessary to achieve 95% power (alpha = 0.05) for Aim 1 assuming a small effect size (Cohen's  $d = 0.1$ ) and an intra-cluster correlation (ICC) equal to 0.7. The sample size estimate was 200. For this calculation, we used an F-test on the interaction between time (two levels) and treatment arm (two levels) in a two-way ANOVA with repeated measurements (RM-ANOVA). We used a more conservative value of the ICC as compared to the actual estimate from the NETworks trial data (ICC = 0.9), as the latter would have resulted in a much smaller sample size (for a larger ICC, the residual sum of squares decreases, therefore precision increases and sample size decreases. The opposite is true when the test is strictly between subjects). Further, we assumed an attrition rate between 15 and 20%, and increased the sample size to 240. Thus, we aim to recruit a total of 240 participants (~120 per cohort), with the initial randomization assigning 120 to SocialPOD+points and 120 to SocialPOD-points.

Based on pilot study for overall app usage (Social POD  $50.7 \pm 25.0$  days and standard  $34.4 \pm 25.8$  days out of a possible 84 days) and points earned (mean of  $202 \pm 105$  points/participant with estimated 50 point difference between groups), our power for Aim 2 will be 99% for app usage and 95% for points earned based on our sample size from Aim 1.

We plan to use a random-effects (RE) model which is mathematically equivalent to repeated-measures-ANOVA. However, in the presence of loss to follow-up, RE models can handle responses that are missing at random. RE models can be adjusted for additional covariates if needed (though the randomization procedure should make this unnecessary). RE models provide additional information about the variance of the random effects which is valuable for understanding heterogeneity of responses and assessing the intra-cluster correlation (ICC).

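### The 99% power for app usage comes from a pilot contrast with a standard app and is not shown to apply to points versus no points within the same social app.

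*Combined protocol and SAP*

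**What the plan says.** Under Statistical Design and Power (Aims 1 and 2), the plan says "we are powering Aim 2 from both differences in overall app usage (Social POD" arm 50.7 days, SD 25.0; standard arm 34.4 days, SD 25.8; 84 days possible) and from points earned. It concludes there that "power for Aim 2 will be 99% for app usage and 95% for points earned". The section Sample size according to F-test repeats this: "our power for Aim 2 will be 99% for app usage and 95% for points earned based on our sample size from Aim 1".

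The pilot is described under Pilot study main results. The team "developed a mobile app that rewards social support through social gaming", and its users "lost more weight (-5.3 kg) than the standard app group". The features of that standard app are not listed.

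The present trial makes a narrower comparison. Study aims gives as a goal "to isolate the use of points to gamify the intervention". Overview of Intervention says "Both groups will receive the same intervention, but in order to isolate the impact of points/social gaming", only one arm is awarded points. Intervention components procedures and Social support activities and gamification describe one app with a newsfeed, thumbs-up, support requests and outreach messages. The arms differ in what is displayed: "The mLife group is unable to see the points earned; they have daily checklists". The power and analysis sections also call the control SocialPOD-points, that is, the social app with points removed.

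**The concern.** A power figure belongs to a particular contrast. The 16.3-day pilot difference is for an app with gamified social support against a standard app. In this trial the social features are in both arms, so any usage they generate should largely cancel, leaving only what the points and leaderboard add. The plan nevertheless carries over the full pilot difference, with no reduction and no argument that points alone would reproduce it. In effect it assigns 34.4 days, the pilot's standard-app figure, to a control arm that uses the social app.

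The app-usage figure is one of two supports offered for the statement that Aim 2 has abundant power. Secondary Aims also asks whether points sustain engagement. A reader who relies on 99% could take a null usage result as near-conclusive against points, when power for that contrast is unknown.

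**Working it through.** **Inputs.** From Statistical Design and Power, Aims 1 and 2: means 50.7 and 34.4 days; SDs 25.0 and 25.8; 240 randomized (120 per arm); 200 before the attrition allowance (100 per arm). Alpha 0.05 is stated for Aim 1 and assumed here for Aim 2. A two-sided test is also assumed. Power is from the noncentral t distribution for two independent means.

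**Step 1: reproduce the plan's figure.**
- Difference = 50.7 − 34.4 = 16.3 days.
- Pooled SD = √((25.0² + 25.8²)/2) = 25.40 days.
- Standardized difference d = 16.3/25.40 = 0.642.
- Noncentrality = d·√(n/2): 0.642 × √60 = 4.97 at 120 per arm; 0.642 × √50 = 4.54 at 100 per arm.
- Power = 99.9% at N=240 and 99.5% at N=200.

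This agrees with the stated 99%, so the full pilot difference is its source.

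**Step 2: what the 99% requires of points alone.** Solving for the difference that gives 99% power with SD 25.40:
- N=240: 14.1 days, and 14.1/16.3 = 87% of the pilot difference.
- N=200: 15.5 days, and 15.5/16.3 = 95% of it.

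**Step 3: power over a range of shares.** The documents do not say how much of the 16.3 days is due to points, so the shares below are assumptions.

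| Assumed share | Difference (days) | Power, N=240 | Power, N=200 |
|---|---|---|---|
| 100% | 16.3 | 99.9% | 99.5% |
| 75% | 12.2 | 96% | 92% |
| 50% | 8.2 | 70% | 62% |
| 25% | 4.1 | 24% | 20% |

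**Step 4: detectable difference.** With SD 25.40 days on the pilot's 84-day scale:
- 80% power: 9.2 days at N=240; 10.1 days at N=200.
- 90% power: 10.7 days at N=240; 11.7 days at N=200.

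**Step 5: is 16.3 days a ceiling?** If the arm sizes under Pilot study main results (26 and 25) also apply to the usage data, the standard error is 25.4 × √(1/26 + 1/25) = 7.1 days. The 95% interval is 16.3 ± 1.96 × 7.1, about 2 to 30 days. The pilot estimate is too imprecise to serve as a bound.

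**The case against.** The strongest reply is that the premise is partly inferred. Nothing in the documents lists the standard app's features, and the word alone does not prove that it lacked social features. Randomization Procedure even codes one arm of this trial as Standard. This stands to the extent that no shortfall in power can be demonstrated; at a 75% share, power is still 92% to 96%. It does not rescue the 99%. The same Randomization Procedure section defines the control as the non-gamified version of mLife, and the plan nowhere argues that points alone would yield nearly the whole pilot difference.

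A second reply is that little depends on app usage. This is largely right. The sample size was set by Aim 1. The Analysis Plan models total points earned and mean support ratings for Aim 2, not days of use. The adequate-power claim also has the points-earned calculation behind it, which uses a separately assumed 50-point difference (SD 105). No passage says how a null usage result would be interpreted.

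A third reply concerns the replacement figures. They use the SD of an 84-day measure, while this intervention runs 12 months. That also stands, so the figures must carry that condition.

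A reader might go further and infer that the trial is underpowered for usage, or that 16.3 days is the most points could achieve. The documents support neither: the share due to points is unknown, and the pilot interval in Step 5 is wide.

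**Conclusion.** The concern holds in a limited form. The 99% is correct arithmetic for Social POD against a standard app, but is not shown to apply to points against no points. It would hold only if points alone produced about 87% of the pilot difference at N=240, or 95% at N=200. The lower powers in the table depend on assumed shares, a two-sided 0.05 test, and an SD of 25.4 days over 84 days. They show how sensitive the claim is; they do not estimate the trial's actual power.

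The consequence is confined to the stated power and to how a null result on the secondary engagement question is read. It would be wrong to infer that the total sample size or the Aim 2 analysis is compromised, since neither rests on the usage figure.

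**What to change.** In both power passages (Aims 1 and 2, and Sample size according to F-test):

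- Remove the 99% as the stated power for app usage under points versus no points, and stop citing usage in support of the abundant-power statement. The points-earned figure is not affected by this point.
- State that the 16.3 days came from a comparison with a standard app, and that the usage effect of points alone is unknown. Do not describe 16.3 days as an upper bound.
- Give instead the detectable differences from Step 4, labelled as conditional on the pilot SD of 25.4 days and an 84-day usage window. Do not apply them to 12-month usage without an SD on that scale.
- Read a null result for usage over a matching window against the detectable difference, not against a claim of 99% power.

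The cost is a few sentences. No participants, data or procedures change; the stated case for usage simply becomes less favourable.

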### **III. Below describes our plans for interim and final analyses and methods for handling missing data:**

#### ***Aims 1 and 2***

Data from all study measures will undergo initial data cleaning to identify potential outliers, determine distributions of variables, assess normality, and enumerate loss to follow-up and other missing data. Descriptive statistics at baseline will be compared between treatment groups to evaluate the success of randomization. ***Analyzing changes in weight between groups at year one***

***(Primary Aims 1):*** For Aim 1, the two levels of the treatment effect will be assignment to SocialPOD+points vs. SocialPOD-points, and the entire study sample will be included. Primary Aim 1 will be addressed using a repeated-measures mixed model with maximum likelihood estimation as provided by PROC MIXED in the SAS® system. Under the assumption that missing data are missing at random, mixed models provide unbiased estimates. These will be adjusted using robust computation of standard errors if non-normality is detected. These models will be estimated applying an intent-to-treat principle. Models for each primary aim are of the same form, with the difference of the groups being compared. Models will examine weight at baseline and at 12 months with a two-level time effect, two-level treatment effect, and two-way interaction between time and treatment. The repeated-measures model will contain time, treatment, time-by-treatment interactions, and any covariates associated with weight loss. Models will be adjusted for changes in PA (via

accelerometers). If the time-by-treatment interaction in a model is significant at the 0.05 level, this will be interpreted as a significant weight-loss effect for one treatment relative to the other.

**Analyzing differences in social support provision and receipt between groups (Aim 2):** For Aim 2, the model will regress support provided (total points earned) and social support received (mean of ratings of support provided to the individual over the 12 months) on treatment group, adjusted for the same covariates used in Aim 1.

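### The stated Aim 2 power (95% for points, 99% for app usage) does not apply to the Aim 2 analysis: the inputs come from a three-month pilot, attrition is ignored, and support received has no power figure

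*Combined protocol and SAP*

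**What the plan says.** Under Statistical Design and Power (Aims 1 and 2), the sample size of 240 is set by Aim 1: 200 evaluable, raised for 15-20% attrition. For Aim 2 the same section states: "This sample size will also give us abundant power for the study in Aim 2". It gives two bases:

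- App usage in the Social POD pilot: 50.7 ± 25.0 against 34.4 ± 25.8 days, "out of a possible 84 days". Stated power is 99%.
- Points earned, standing for support provision. Pilot participants earned 202 ± 105 points, and the plan then says "We are assuming a difference of 50 points between groups with a SD of 105". Stated power is 95%.

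The section Sample size according to F-test repeats both ("points/participant with estimated 50 point difference between groups"). The power section closes by saying that the sample size was chosen to give sufficient power for provision and receipt at one year.

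The synopsis describes the pilot as "a three-month randomized weight loss intervention". Of the present trial it says "The intervention will last 12 months". Analysis Plan III defines two Aim 2 outcomes: total points earned (provision) and the mean of the support ratings over the 12 months (receipt). Usage patterns over time are listed under Secondary Aims.

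**The concern.** A power figure supports an aim only if its inputs describe the outcome that will be tested. Four things do not match here.

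1. Points accumulate day by day, up to 8 per day. A difference and an SD from a three-month total are not those of a 12-month total, and the plan rescales neither. For weight, the F-test section chose a pilot with one-year data because the main outcomes are at 12 months. It did not do the same for points.
2. The attrition built into the sample size is not carried into the Aim 2 power.
3. One of the two power figures is for a variable outside the Aim 2 model.
4. One of the two Aim 2 outcomes has no power figure.

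Aim 2 is a primary aim. If it shows no difference, a reader would rely on the stated 95% and 99% to decide how informative that result is.

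**Working it through.** **Inputs from the documents.** Points: difference 50, SD 105, so d = 50/105 = 0.476. App usage: difference 50.7 − 34.4 = 16.3 days, pooled SD = √[(25.0² + 25.8²)/2] = 25.4, so d = 0.64. Randomised: 120 per arm. Attrition of 15-20% leaves 102 to 96 per arm; the plan's evaluable target of 200 is 100 per arm.

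**Assumption.** Two-sided alpha 0.05; the plan states 0.05 for Aim 1 only.

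**Method.** Two-sample t-test with n per arm, noncentrality λ = d√(n/2) and 2n − 2 degrees of freedom.

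**Step 1: the plan's own figures.**

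| n per arm | Points (d = 0.476) | App usage (d = 0.64) |
|---|---|---|
| 120 | 95.7% | 99.9% |
| 102 | 92.3% | 99.5% |
| 100 | 91.8% | 99.5% |
| 96 | 90.7% | 99.3% |

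For points, λ = 0.476 × √60 = 3.69 at 120 per arm and 0.476 × √50 = 3.37 at 100. The stated 95% is reproduced only with nobody lost. The stated 99% for app usage is reproduced at every n.

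**Step 2: time scale.** The documents attach the 84 days to app usage. That the 202 ± 105 points cover the same period is inferred from the pilot's three months. The ratio of durations is 365/84 = 4.35. Two simple scalings of the SD, for illustration:

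- independent periods: 105 × √4.35 = 219
- fully correlated periods: 105 × 4.35 = 456

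If the daily difference persists, the difference becomes 50 × 4.35 = 217. At 100 per arm:

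| 12-month difference | 12-month SD | d | Power |
|---|---|---|---|
| 50 | 456 | 0.11 | 12% |
| 50 | 219 | 0.23 | 36% |
| 217 | 456 | 0.476 | 92% |
| 217 | 219 | 0.99 | above 99.9% |

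In the third row the scaling changes nothing; the fall from about 96% to 92% comes only from using 100 instead of 120 per arm. For 95% power at 100 per arm the 12-month difference would have to be about 112 points (SD 219) or 234 points (SD 456).

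**Step 3: support received.** Without a difference or SD, only a detectable standardised difference can be given. At 100 per arm it is (1.960 + 1.645) × √(2/100) = 0.51 SD for 95% power and (1.960 + 0.842) × √(2/100) = 0.40 SD for 80%.

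**The case against.** The arithmetic is sound on its own inputs: both stated figures are reproduced at 120 per arm. The 50 points carry no time frame, and if the difference and the SD grow together, power does not change. A sustained effect could be ample. Fifty points over 84 days is 0.60 per day, and the 112 to 234 points needed for 95% power amount to 0.31 to 0.64 per day over 365 days. All of this stands.

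For the same reason, a reader might infer from the 12% and 36% rows that Aim 2 is underpowered. The documents do not support that. Those rows hold the difference at 50, as if the arms gained no further separation after the pilot window, while the SD grows. A reader might also conclude that a 12-month SD of 105 is impossible, or that 219 and 456 are limits. Neither follows, because the SD depends on how participants differ from one another over the year, and the plan gives no data on that. The 12-month window for total points is itself a reading: the analysis plan attaches that period to the ratings, and for points it follows from Aim 2 and the length of the intervention.

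On attrition, the app computes points in both arms, so a missed assessment need not remove a points total. However, accounts of withdrawn and excluded participants are inactivated. The evaluable number is therefore open to argument and should be stated. A one-sided 0.05 test would give 95.7% at 100 per arm (normal approximation), but neither power section states such a test.

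The plan openly names app usage as a basis for powering Aim 2. That does not make it an Aim 2 outcome. Finally, Aim 1 set the sample size and recruitment of both cohorts has begun, so nothing in the Aim 2 test or the number enrolled would change. That limits the consequence but does not make the power statement correct.

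**Conclusion.** The concern holds in this form: the plan does not demonstrate the power that it claims for Aim 2.

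- **Points, time scale.** Power for a 12-month total cannot be determined from the documents. The illustrative values run from 12% to above 99.9% at 100 per arm and are not bounds. They rest on a two-sided 0.05 test and on the inferred pilot window.
- **Points, attrition.** This part needs no assumption about time. On the plan's own d of 0.476, the 95% should read about 91-92% once 15-20% are lost, unless the plan explains why points totals would remain complete.
- **App usage.** The 99% is correct arithmetic for a secondary-aim variable and says nothing about the Aim 2 model.
- **Support received.** No power is given, although the section says that the sample size secures it.

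The power statement is wrong as written. The documents do not show that Aim 2 is underpowered.

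**What to change.** Rewrite the Aim 2 power paragraph in both places where it appears:

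1. Give the assumed 12-month difference and SD for total points, with their basis, or state outright that a standardised difference of 0.48 is assumed.
2. Replace 95% with power at the post-attrition number (about 91-92% for 0.48), and state how many participants are expected to have a points total.
3. Move the app-usage figure to the secondary aims.
4. For support received, give the detectable standardised difference: about 0.51 SD at 95% power and 0.40 SD at 80%, with 100 per arm.
5. Remove the general claim of ample power for Aim 2 unless the restated figures support it.

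The cost is one rewritten paragraph, repeated in the second section, and no extra participants. The stated power becomes slightly lower and conditional on a named assumption.
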